3.2 Analysis Populations

The analysis populations are defined in Table .

Table 3.2-1 Analysis Populations

Population	Description
As-treated population	Subjects who receive any study investigational product will be included in the as-treated population and subjects will be analyzed according to the treatment they actually receive.
Response evaluable population	The response evaluable population includes all subjects from the As-treated Population who have a baseline disease assessment with measurable disease and one of the following: (1) at least one post-baseline disease assessment, and/or (2) withdrawn from study treatment prior to post-baseline disease assessment due to clinical progression or death.
DLT evaluable population	The DLT evaluable population includes all subjects enrolled in Phase 1b who receive the protocol-assigned treatment and complete safety follow-up through the DLT evaluation period or experience a DLT during the DLT evaluation period.

Table 3.2-1 Analysis Populations

Population	Description
Crossover population	Crossover population includes all subjects who crossover to receive combination therapy (MEDI4736 in combination with tremelimumab) after confirmed progression on the initial treatment assignment of MEDI4736 or tremelimumab monotherapy.
Re-treated population	Re-treated population includes all subjects who have been re-treated with combination therapy (MEDI4736 in combination with tremelimumab) during the first 12 months of follow-up.

If the number of subjects in the re-treatment population or crossover population is too small (e.g. ≤ 5), the planned analysis for the re-treatment phase may be reduced and simplified. Details will be presented in the statistical programming plan (SPP).

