4.8 Statistical Evaluation

4.8.1 General Considerations

For the purpose of generating the clinical study report, the primary analysis for this study may occur after all subjects in corresponding arms have either discontinued from the study or been on the study for at least 7 months (Arms, A, B, C, and E) or 5 months (Arm D). Final analyses for this study including selected efficacy/safety endpoints (if primary analysis occurred) will occur after study closure. The study populations are defined as follows:

- DLT Evaluable Population is defined as subjects enrolled in Phase 1b who receive the protocol-assigned treatment and complete safety follow-up through the DLT evaluation period (Section 3.1.3.2) or experience a DLT during the DLT evaluation period.
- As-treated Population is defined as subjects who receive any dose of either investigational product(s).
- Response Evaluable Population is defined as all subjects from the As-treated Population who have a baseline disease assessment with measurable disease and one of the following: (1) at least one post-baseline disease assessment, and/or (2) withdrawn from study treatment prior to post-baseline disease assessment due to clinical progression or death.
- Crossover Population is defined as all subjects who crossover to receive combination therapy (MEDI4736 in combination with tremelimumab) after confirmed progression on the initial treatment assignment of MEDI4736 or tremelimumab monotherapy.
- Re-treated Population is defined as all subjects who have been re-treated with combination therapy (MEDI4736 in combination with tremelimumab) during the first 12 months of follow-up.

Tabular summaries will be presented by treatment group. Categorical data will be summarized by the number and percentage of subjects in each category. Continuous variables will be summarized by descriptive statistics. Analyses may be performed for the crossover and the re-treated populations (if warranted by data). Additional details of statistical analyses will be described in the statistical analysis plan.

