4.8.3 Efficacy

The efficacy analysis will be based on the As-treated Population. Sensitivity analyses for response-related endpoints (OR, DoR, and DC) will be performed based on the Response Evaluable Population.

The following response-related endpoints and corresponding time-to-event endpoints for primary and secondary efficacy endpoints programmatically-derived from the investigator's assessments or BICR, as well as OS, will be analyzed. More details will be provided in the statistical analysis plan.

- OR is defined as best overall response of confirmed CR or confirmed PR according to RECIST v1.1. The best overall response is defined as the best response (in the order of CR, PR, SD, PD, and not evaluable) among all overall responses recorded from the start of treatment/until progression, or the last evaluable disease assessment in the absence of PD prior to the initiation of subsequent anticancer therapy or discontinuation from the study, whichever occurs first. The best overall response of CR or PR must be confirmed, which means a response of CR/PR is recorded at 1 visit and confirmed by repeat imaging not less than 28 days (4 weeks) after the visit when the response was first observed with no evidence of progression between the initial and CR/PR confirmation visit.
- DoR is defined as the duration from the first documentation of OR to the first documented disease progression according to RECIST v1.1 or death due to any cause, whichever occurs first. For subjects who are alive and progression-free at the time of DCO for analysis, DoR will be censored at the last tumor assessment date. The DoR will be evaluated only for the subjects with an OR.
- DC is defined as confirmed CR, confirmed PR, or SD based on RECIST v1.1. DC at 16 and 24 weeks is defined as a best overall response of confirmed CR, confirmed PR or having SD with duration of SD lasting 16 and 24 weeks, respectively.
- PFS will be measured from the date of randomization or start of treatment until the documentation of disease progression according to RECIST v1.1 or death due to any cause, whichever occurs first. For subjects who are alive and progression-free at the time of DCO for analysis, PFS will be censored at the last tumor assessment date. PFS-6 and [REDACTED] are the proportion of subjects with PFS at 6 months [REDACTED], respectively.

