3.4.1 Primary Efficacy Endpoints and Analyses

Arms A, B, C and E

The two co-primary efficacy endpoints are Objective response (OR) and PFS-6 based on RECIST v1.1.

Arm D

The primary efficacy endpoint is objective response (OR) based on RECIST v1.1.

The primary efficacy analyses for the primary efficacy endpoint(s) will be based on the As-treated Population.

Objective Response

Objective response (OR) is defined as best overall response (BOR) of confirmed CR or confirmed PR according to RECIST v1.1. The best overall response is defined as the best response (in the order of CR, PR, SD, PD, and not evaluable) among all overall responses recorded from the date of randomization for Phase 2 Arm A, B and C subjects or the date of first dose of study treatment for Phase 1b and Phase 2 Arm D and E subjects until progression, or the last evaluable disease assessment in the absence of PD prior to the initiation of subsequent anticancer therapy or discontinuation from the study, whichever occurs first.

The best overall response (BOR) of CR or PR must be confirmed, which means a response of CR/PR is recorded at 1 visit and confirmed by repeat imaging not less than 28 days (4 weeks) after the visit when the response was first observed with no evidence of progression between the initial and CR/PR confirmation visit. A confirmed CR is defined as two CRs that were

separated by at least 28 days with no evidence of progression in-between. A confirmed PR is defined as two PRs or an un-confirmed PR and an un-confirmed CR that were separated by at least 28 days with no evidence of progression in-between. For a subject to qualify for a BOR of SD, at least 54 days from the randomization date or start of treatment date must elapse without disease progression. The definition of 54 days reflects the protocol-defined disease assessment window of ± 3 days (Day 57 plus/minus 3 days).

Subjects who responded with an unconfirmed CR/PR at the time of data cutoff will be reported as CR/PR pending confirmation under the SD category provided the minimum criteria for SD duration (54 days) are met, otherwise this will be reported under the Non Evaluable (NE) category. NE is assigned for a subject who has only a baseline assessment, or a response assessment of CR/PR/SD at an interval of less than 54 days since randomization or the start of treatment and who has no subsequent disease evaluation, or has all overall response evaluations assessed as NE.

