The ORR is defined as the proportion of subjects with OR. The 2-sided 90% and 95% CI of ORR will be estimated based on the exact probability method. In addition, to help make a comparison to historical data, the unconfirmed ORR which is defined as the proportion of subjects who achieved a best overall response of confirmed/unconfirmed CR or confirmed/unconfirmed PR will be presented along with its CI.

ORR will be compared between the three treatment groups (Arm A, B and C). P-values will be presented without multiplicity adjustment. The comparisons will include the following:

- MEDI4736 + tremelimumab combination therapy (Arm A) versus MEDI4736 monotherapy (Arm B)
- MEDI4736 + tremelimumab combination therapy (Arm A) versus tremelimumab monotherapy (Arm C)

P-values for comparisons of ORR between the treatment groups mentioned above will be obtained from Fisher's exact test. The statistical significant treatment difference will be tested against 2-sided alpha level of 0.05. In addition, the difference in ORR between MEDI4736 + tremelimumab combination and MEDI4736 monotherapy or tremelimumab and associated 95% exact unconditional confidence interval will be provided using Agresti and Ming (2001)'s approach by specifying the RISKDIFF(METHOD=FMSCORE) option in PROC FREQ.

PFS-6

PFS-6 is 6-month progression-free survival rates, which is the proportion of subjects who are progression free and alive at 6 months. PFS is defined as the time from the date of randomization for Phase 2 Arm A, B and C subjects or the date of first dose of study treatment for Phase 1b and Phase 2 Arm D and E subjects to the earlier of the dates of the first objective documentation of radiographic disease progression (per RECIST v1.1) or death due to any cause.

For subjects who are alive with no objective documentation of (radiographic) disease progression by the data cutoff date, PFS will be censored at the date of their last evaluable tumor assessment. If the subject progresses or dies after ≥ 2 consecutively missed or non-evaluable disease assessment visits, PFS will be censored at the time of the latest evaluable disease assessment prior to the missed assessments.

In this study, progression or death after ≥ 2 consecutive missed disease assessment visits is defined (according to disease assessment schedules specified in the protocol) as below:

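### The A vs B and A vs C comparisons of ORR and PFS-6 are between randomised open-label arms, but are run on dosed subjects grouped by treatment received; add an all-randomised analysis for these two contrasts

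*SAP*

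**What the plan says.** SAP 3.4.1 sets up formal between-arm comparisons: "ORR will be compared between the three treatment groups (Arm A, B and C"), as A vs B and A vs C, by Fisher's exact test against a 2-sided 0.05 level. PFS-6 is compared for the same two pairs using log-log transformed Kaplan-Meier estimates. Neither set of p-values is adjusted for multiplicity.

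The analysis set is stated in the same section: "The primary efficacy analyses for the primary efficacy endpoint(s) will be based on the As-treated Population". SAP Table 3.2-1 limits that population to subjects who received investigational product and adds the grouping rule: "subjects will be analyzed according to the treatment they actually receive". Protocol 4.8.3 also uses it ("The efficacy analysis will be based on the As-treated Population"), but the protocol's definition in 4.8.1 rests on receipt of any dose and contains no grouping rule; only the SAP adds one.

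The sensitivity set for response endpoints is narrower still: "The response evaluable population includes all subjects from the As-treated Population who have a baseline disease assessment with measurable disease", with further conditions. Table 3.2-1 lists no intent-to-treat or all-randomised population.

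The SAP does keep randomisation as the time origin: "PFS is defined as the time from the date of randomization for Phase 2 Arm A, B and C subjects". Protocol 4.6.1 requires treatment to start no more than 1 business day after randomisation, and 4.6.2 confirms that the study is open-label. Protocol 3.1.2.4 lets Arm B and C subjects cross over to the combination after confirmed progression.

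**The concern.** A comparison of randomised arms is protected by analysing everyone who was randomised, in the arm assigned. This plan departs from that in two ways, both after the assignment is known to subject and site. Undosed subjects leave the analysis, and anyone given something other than the assigned regimen is counted in another arm. Either event can depend on the arm, and the p-value then no longer tests the randomised contrast. The planned sensitivity set cannot reveal the effect, because it starts from As-treated.

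The grouping rule is also incomplete. Because crossover to the combination is allowed, the phrase about treatment received needs to say that it means initial treatment. For ORR and PFS under RECIST v1.1, progression has already closed the endpoint before crossover, so that is the sensible reading, but the SAP does not state it.

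At stake are the ORR and PFS-6 contrasts of the combination against each monotherapy in small arms, where a few subjects can move a result across a stated threshold.

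**Working it through.** **The plan's own figure.** SAP 2.4.2 gives 85% power for Arm A vs Arm C, 35% vs 10%, 1-sided alpha 0.10.

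- Evaluable numbers: 125 × 0.4 × 0.9 = 45; 125 × 0.2 × 0.9 = 22.5, taken as 22.
- Pooled rate = (45 × 0.35 + 22 × 0.10)/67 = 0.268.
- Null standard error = √[0.268 × 0.732 × (1/45 + 1/22)] = 0.1152.
- Alternative standard error = √[0.35 × 0.65/45 + 0.10 × 0.90/22] = 0.0956.
- Power = Φ[(0.25 − 1.2816 × 0.1152)/0.0956] = Φ(1.07) = 85.8%.

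The stated power reproduces and is not disputed. The point concerns who is analysed.

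**Shift in the ORR difference.** The documents give no count of undosed subjects, so the counts here are assumptions. Take the planned 50 and 25, 35% and 10% ORR among dosed subjects, and count undosed subjects as non-responders:

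| Undosed in A | Undosed in C | A as randomised | C as randomised | Difference (points) |
|---|---|---|---|---|
| 0 | 0 | 35.0% | 10.0% | 25.0 |
| 2 | 0 | 0.35 × 48/50 = 33.6% | 10.0% | 23.6 |
| 0 | 2 | 35.0% | 0.10 × 23/25 = 9.2% | 25.8 |
| 2 | 2 | 33.6% | 9.2% | 24.4 |

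As-treated gives 25.0 in every row. The shift is at most 1.4 points and can go either way.

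**Effect on the ORR test, planned sizes (two-sided Fisher).**

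- 18/50 vs 3/25: p = 0.032. Drop one undosed Arm C subject, 18/50 vs 3/24: p = 0.053.
- 17/50 vs 3/25: p = 0.054. Drop four undosed Arm A subjects, 17/46 vs 3/25: p = 0.030. Dropping three (17/47) leaves p = 0.051.
- 17/50 vs 3/25: p = 0.054. Regroup one Arm C responder who received the combination, 18/51 vs 2/24: p = 0.023.

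**Effect at the sizes probably reached.** Arm counts are redacted. Protocol 3.1.1 gives 89 enrolled in Arms A to D. If Arm D enrolled its planned 25 (assumption), 89 − 25 = 64 remain; split 2:2:1 that is 25.6, 25.6 and 12.8, or about 26, 26 and 13.

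- 8/26 vs 0/13: p = 0.035. One Arm C exclusion (0/12): p = 0.039. Two (0/11): p = 0.076.
- 7/26 vs 0/13: p = 0.073. One Arm A exclusion (7/25): p = 0.072. Two (7/24): p = 0.038.
- 7/26 vs 1/13: p = 0.23. Two Arm A exclusions (7/24 vs 1/13): p = 0.22.

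In these examples one exclusion changes no conclusion. Two are needed, with no Arm C responders; two subjects are 2/13 = 15% of Arm C.

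**PFS-6.** An undosed subject who withdraws has no assessment after first dose. The last row of SAP Table 3.4.1-1 then censors at randomisation. Such a subject is never at risk after time zero, so the Kaplan-Meier estimate at 6 months and its Greenwood variance do not change. Adding undosed subjects back matters for PFS-6 only if an early death or later scans are recorded. Correcting the group of a mis-dosed subject would matter in any case.

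**The case against.** The strongest reply is that the problem may be empty in practice. Dosing is due within 1 business day of randomisation, and the study monitor must be told at once of any delay. Table 4.2.2-1 places randomisation/enrolment on Week 1 Day 1. Few subjects can be randomised and never dosed, and the documents report none. This stands, and it also answers a stronger reading that a reader might infer: that timing PFS from randomisation in a dosed-only set builds in a material mismatch. A gap of about a day cannot do that.

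A reader might also infer that the rule favours the combination. The documents do not support that. Losing Arm C non-responders raises the Arm C rate and weakens the A vs C result; losing Arm A non-responders does the reverse.

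Second, these comparisons are not confirmatory: sizing rests mainly on precision, p-values are unadjusted, and Arms A to C were closed early at the sponsor's discretion. This also stands and limits the weight of the point. The SAP nevertheless sets a significance level and a power statement for A vs C, so the comparison will be read as a test.

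Third, the plan may cover this elsewhere. SAP 3.3.1 tabulates subjects randomised or treated by arm, which could expose an imbalance in undosed subjects, though it does not correct the comparison. Protocol 4.8.3.4, Sensitivity Analyses, appears in the contents but its text is not in the public copy, and SAP 3.4.4 ends in a redaction. An as-randomised sensitivity analysis there cannot be excluded. The primary set is clear regardless.

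Finally, As-treated is the protocol's own choice for efficacy, so the remedy goes beyond SAP wording. That is correct and is counted in the cost.

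**Conclusion.** The point holds in limited form. The two randomised contrasts are analysed on dosed subjects by treatment received, with no all-randomised set visible and a sensitivity set that cannot recover exclusions. That leaves the comparisons open to avoidable bias, in either direction.

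The likely size is small. If every subject was dosed as assigned, results are identical. Undosed subjects who withdraw hardly affect PFS-6, so ORR is the main exposure, with mis-dosing relevant to both endpoints. At planned sizes one subject can carry an ORR result across 0.05 in a chosen example; at about 26 vs 13 the examples need two exclusions and no Arm C responders. These figures rest on assumed responder and undosed counts, and the smaller sizes also assume that Arm D enrolled its planned 25. They show sensitivity and predict nothing about what happened.

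A reader might conclude that the A vs B and A vs C results are invalid. The documents do not support that: no undosed or mis-dosed subject is reported, and the comparisons are exploratory. This is an inexpensive improvement to the plan.

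**What to change.** For the A vs B and A vs C comparisons only:

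- Define an all-randomised set grouped by assigned arm.
- For ORR, count undosed subjects as non-responders.
- For PFS-6, apply the existing event and censoring rules from randomisation.
- Report the number undosed and the number mis-dosed in each arm.
- Show the As-treated result alongside. With both reported, the change cannot be taken for a choice made after the arms closed.

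Keep As-treated as the main set for single-arm estimates, Arms D and E, and safety. In SAP Table 3.2-1, state that treatment received means the initial treatment and not treatment after crossover.

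Cost: a few lines in SAP 3.2 and 3.4.1, one extra run of existing programs, and a conforming note to protocol 4.8.3, which names As-treated for efficacy. Treatment is assigned through the IXRS, so assigned arm should already be on record. If nobody was undosed or mis-dosed, the extra run shows it and the question is closed.

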3.3 Study Subjects

3.3.1 Subject Disposition and Completion Status

A summary of subjects treated at each dose level in Phase 1b as well as subjects randomized or treated at each treatment arm in Phase 2 will be provided. In addition, summaries using the number and percent of subjects that completed or discontinued treatment and the reasons for discontinuation during the initial treatment and re-treatment will be provided.

Summaries using the number and percent of subject status at the end of study and the reasons for ending study will be provided. For the subjects who end the study due to withdrawal of consent, the reason for withdrawal will be summarized.

The end of study mortality summary will include subjects who are dead at the end of study and their cause of death (e.g., toxicity related to investigational product or disease under investigation).

3.3.2 Demographics and Baseline Characteristics

Demographic information and baseline disease characteristics will be summarized for the As-treated population. Demographic information related to sex, age, race, ethnicity, weight, height, and body mass index will be summarized. Tumor diagnosis including disease stage, extent of disease at study entry, time from initial diagnosis to study entry, MSI testing gene status (present/absent), EBV evaluation of the tumor status (positive/negative), helicobacter pylori status (positive/negative), anatomic location of primary tumor, histology subtype and number of organs involved with metastasis will be summarized.

The summary for prior anticancer treatment will include the number and percent of subjects by: lines of therapy for recurrent/metastatic disease, treatment setting, type of treatment (i.e. biologic, immunotherapy, radiotherapy, chemotherapy, surgery, and other), and best response (complete response, partial response, stable disease, progressive disease, not evaluable, and not applicable) to the most recent line of therapy.

Baseline tumor characteristics including number and sites of target and non-target tumor lesions as well as tumor burden (sum of target lesion diameters) will be summarized.

3.3.3 Study Drug Exposure

The number of MEDI4736 and tremelimumab doses/cycles and total MEDI4736 and tremelimumab duration of exposure will be summarized by descriptive statistics and by frequency. [REDACTED]

[REDACTED]

Number of doses is defined as the total number of doses received. A dose will be counted if treatment is started even if the full dose is not delivered. The dose intensity (mg/kg/cycle length) is defined as total actual dose (in mg/kg) that a subject received per study defined cycle. Relative dose intensity is defined as the dose intensity divided by the planned dose per cycle. The details of the dose intensity calculation will be provided in the SPP.

Dosing delays, interruptions and omissions of MEDI4736 and tremelimumab will be derived based on the scheduled dosing dates and will be summarized.

3.3.4 Concomitant Medications

The number and percentage of subjects who took at least 1 dose of medication other than investigational product(s) during the study will be summarized by the ATC class and preferred term coded by AstraZeneca Drug Dictionary (AZDD) for each treatment group. The summary table of concomitant medications will include all concomitant medications taken on or after the date of first dose of investigational products or any concomitant medication started prior to first dose of study treatment that continued beyond the date of first dose of investigational products.

